13.4 Vital Signs

Vital signs (systolic blood pressure, diastolic blood pressure, heart rate, pulse oximetry, and temperature) and weight will be summarized using descriptive statistics at baseline and at each post-baseline time point (the Day 28, 58 and 84 visit and Day 84/EOT) as well as for the most extreme result (high and low). Changes from baseline will also be summarized.

Incidence of PCS events will be presented by time point and for the most extreme post-baseline value at any visit (including unscheduled results).

Table 12.4 Vital Sign PCS Thresholds

Criteria for Treatment Emergent PCS Vital Signs

Vital Sign Parameter	Flag	Criterion Value	Change from Baseline
Systolic Blood Pressure (mmHg)	High (CH)	≥ 180	Increase of ≥ 20 mmHg
	Low (CL)	≤ 90	Decrease of ≥ 20 mmHg
Diastolic Blood Pressure (mmHg)	High (CH)	≥ 105	Increase of ≥ 15 mmHg
	Low (CL)	≤ 50	Decrease of ≥ 15 mmHg
Heart Rate (bpm)	High (CH)	≥ 120	Increase of ≥ 15 bpm
	Low (CL)	≤ 50	Decrease of ≥ 15 bpm
Temperature (°C)	Low (CL)	<36.0	NA
	High (CH)	>38.0	NA

bpm=beats per minute; C=Celsius; DBP=diastolic blood pressure; SBP=systolic blood pressure

13.5 Physical Examination

Physical examination results will be included in data listings only.

13.6 Electrocardiogram

Overall interpretation results for ECGs will be summarized using shift tables (normal, abnormal not clinically significant, and abnormal clinically significant) comparing baseline to EOT.

Descriptive statistics at baseline and at each post-baseline time point (the Day 84 visit, and Day 84/EOT), as well as changes from baseline, will be summarized for each ECG parameter (ventricular rate, RR, PR, QRS, QT, QTcF).

In addition, a categorical summary of abnormal corrected QT interval (QTc) values will be presented. At each time point, the number of subjects with QTc according to Fridericia's formula ($QTcF = QT/(RR^{1/3})$ (seconds)) and exceeding the thresholds below will be presented.

Table 12.6 ECG PCS Thresholds

ECG Parameter	PCS threshold
QTc (high), unadjusted and Fridericia's	>450 msec
	>480 msec
	>500 msec
QTc (increase), unadjusted and Fridericia's	>30 msec from baseline
	>60 msec from baseline

Source is ICH E14 ECG QTcF category thresholds.

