7. NOTATION OF TREATMENT GROUPS AND VISITS

Table 7.1.1 Notation of Treatment Groups

The following notation of treatment groups will be used throughout the report:

Full notation (as used in the study protocol)	Notation used throughout all tables, listings, and figures
300 mg oral omadacycline	Omadacycline 300 mg
Placebo	Placebo

Table 7.1.2 Visit Terminology

Visit	Notation used throughout all tables, listings, and figures
Screening	Screening
Day 1 Baseline	Day 1 (in Listings)/ Baseline (in Tables and Figures)
Day 14 Tele-visit (\pm 2d)	Day 14
Day 28 (\pm 3d)	Day 28

Day 56 ($\pm 3d$)	Day 56
Day 84 (+5d/-2d)	Day 84
EOT: defined as the visit occurring when subjects prematurely discontinue treatment (End of Treatment) (+5d/-2d)	EOT (shown on listings)
Day 84/EOT: defined as Day 84 for subjects who complete treatment or the visit occurring when subjects prematurely discontinue treatment (End of Treatment) (+5d/-2d)	Day 84/EOT (shown on tables)
30 Day Safety Follow-up Call (+7d)	Follow-up

EOT = end of treatment

For by visit summaries, the nominal visit will be summarized. If there is no nominal visit result, unscheduled visits that occur in the protocol defined window will be summarized instead. If multiple unscheduled visits occur in the window, the one closest to the nominal visit date will be used. For sputum cultures, if there are multiple positive cultures on the same day with different MICs to omadacycline, the culture with the highest MIC to omadacycline is used.

Study days corresponding to measurements are calculated as:

- Assessment date – date of first exposure to treatment + 1 (if assessment date is on or after the date of first exposure to treatment)
- Assessment date – date of first exposure to treatment (if assessment date is before the date of first exposure to treatment)

If the date of first exposure to treatment is missing, study days will be calculated by using the randomization date.

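### The ECG interpretation shift table is tied to EOT, which the SAP defines as the early-discontinuation visit only; Table 12.6 also adds an undefined unadjusted QTc to limits meant for QTcF

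*SAP*

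**What the plan says.** SAP 13.6 plans three ECG displays.

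- **Overall interpretation.** A shift table in three categories: "normal, abnormal not clinically significant, and abnormal clinically significant) comparing baseline to EOT".
- **Parameters.** Descriptive statistics and changes from baseline for ventricular rate, RR, PR, QRS, QT and QTcF, at the Day 84 visit and at Day 84/EOT.
- **QTc categories.** The text counts subjects by QTcF. Table 12.6 sets limits of 450, 480 and 500 msec, and increases of 30 and 60 msec. Its first row label begins "QTc (high), unadjusted and" and goes on to name Fridericia; the row for increases is labelled the same way. The footnote reads "Source is ICH E14 ECG QTcF category thresholds".

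SAP Table 7.1.2 fixes the visit terms. One entry is "EOT: defined as the visit occurring when subjects prematurely discontinue treatment (End of Treatment) (+5d/-2d"), with the output label "EOT (shown on listings"). The next is "Day 84/EOT: defined as Day 84 for subjects who complete treatment or the visit occurring when subjects prematurely discontinue treatment", with the output label "Day 84/EOT (shown on tables").

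Protocol 8.7 and Appendix 1 schedule ECGs at Screening and at one combined Day 84/EOT visit.

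**The concern.** The shift-table sentence uses the term that the SAP reserves for early stoppers. A programmer who follows Table 7.1.2 exactly would build a table without the Day 84 ECG of anyone who completed treatment. No other planned summary reports the overall interpretation, so nothing else in the tables would make up for the omission. Early stoppers are also a selected group, and their interpretation shifts need not resemble those of completers.

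The second conflict is within Table 12.6. Text and footnote point to QTcF, while the row labels add a metric that is nowhere defined. An unadjusted QTc contradicts itself, and uncorrected QT is the natural reading. Uncorrected QT lengthens as heart rate falls, so limits drawn up for QTcF would produce counts that partly reflect rate.

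Protocol Section 4 lists ECG change and potentially clinically significant ECGs as primary safety endpoints. Protocol 12.6 leaves the definition of clinical significance to the SAP, and Table 12.6 is where the SAP gives it for ECGs.

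**Working it through.** The plan states no figure on this point, so there is none to reproduce.

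**1. Visit label**

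| Place | Term used | Who is included |
|---|---|---|
| SAP Table 7.1.2, for listings | EOT | early discontinuers |
| SAP Table 7.1.2, for tables | Day 84/EOT | completers and early discontinuers |
| SAP 13.6, parameter summaries | Day 84; Day 84/EOT | completers included |
| SAP 13.6, interpretation shift | EOT | early discontinuers, if read literally |
| SAP 12.3, semi-quantitative culture shift | Days 28, 56, 84 and EOT | completers included, through Day 84 |

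The culture shift table in SAP 12.3 also uses bare EOT, but names Day 84 beside it. The ECG sentence does not name Day 84.

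**2. Size under the literal reading**

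The documents give no discontinuation rate, so the rates here are assumptions. Planned numbers are 45 omadacycline and 30 placebo (SAP Section 5). The number in the table is at most arm size × rate, since an early stopper also needs an ECG at that visit.

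| Assumed rate | Omadacycline in table | Placebo in table | Completers omitted, of 75 |
|---|---|---|---|
| 10% | 45 × 0.10 = 4.5 | 30 × 0.10 = 3 | 67.5 |
| 20% | 45 × 0.20 = 9 | 30 × 0.20 = 6 | 60 |
| 40% | 45 × 0.40 = 18 | 30 × 0.40 = 12 | 45 |

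**3. Heart rate and uncorrected QT**

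The SAP gives QTcF = QT / RR^(1/3), with RR in seconds. Rearranged, QT = QTcF × (60/HR)^(1/3). The QTcF and heart-rate values below are illustrative assumptions.

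Flags created by rate alone:

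- QTcF 430 at 50 bpm: 430 × 1.2^(1/3) = 456.9 msec, above 450.
- QTcF constant at 400, heart rate 80 to 60 bpm: 400 − 400 × 0.75^(1/3) = 36.6 msec, above 30.
- QTcF constant at 420, heart rate 80 to 50 bpm: 420 × [1.2^(1/3) − 0.75^(1/3)] = 64.7 msec, above 60.

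The opposite direction:

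- QTcF 510 at 90 bpm: 510 × (60/90)^(1/3) = 445.5 msec, so QT passes none of the absolute limits. QTcF passes all three and is counted there.
- QTcF 400 to 435 while heart rate goes from 65 to 85 bpm: QT goes from 400 × (60/65)^(1/3) = 389.5 to 435 × (60/85)^(1/3) = 387.3, a fall of 2.2 msec. The QTcF rise of 35 msec is counted above 30.

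The unadjusted counts can therefore gain flags that QTcF does not support. They cannot remove a flag from the QTcF counts, which are tabulated against the same limits.

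**The case against.** The strongest reply is that the SAP resolves the first conflict itself. Table 7.1.2 assigns Day 84/EOT to tables, and a shift table is a table. The next paragraph of SAP 13.6 uses Day 84 and Day 84/EOT, the protocol has a single combined visit, and both abbreviation lists expand EOT simply as end of treatment. The table layouts are in a separate document (SAP Appendix C), which is not available here and may carry the right label. This stands as evidence of a label slip. It does not correct the sentence, which still names the wrong defined term.

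A reader might go further and infer that completers' ECGs are lost to the safety analysis. The documents do not support that. The parameter summaries, changes from baseline and QTcF categories include completers, and those displays serve the ECG endpoints listed in the protocol. Protocol 12.6 does not ask for an interpretation shift table; it is an addition in the SAP.

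A reader might also infer from Table 12.6 that real QTc prolongation could be hidden. That is not supported either, because every QTcF exceedance is counted in its own right. Ventricular rate and RR are summarised too, so a general shift in heart rate would be visible. Finally, reading *unadjusted* as uncorrected QT is an inference: the row label says QTc. What is established is an undefined metric that the governing text and footnote do not mention.

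**Conclusion.** Both conflicts are real and both are minor. The shift-table sentence uses a term that, as defined, excludes completers from the only summary of overall ECG interpretation. How many would be omitted depends on the literal reading and on a discontinuation rate that the documents do not give, so the figures above show scale and are not a forecast. Table 12.6 names a metric that its own text and footnote do not. If that metric is uncorrected QT, the consequence is some rate-driven flags in an extra set of counts. The listed ECG endpoints, the QTcF counts, the efficacy analyses, the sample size and the power are unaffected.

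**What to change.** In SAP 13.6, change the shift-table comparison to baseline versus Day 84/EOT, optionally with Day 84 shown as well, and check that the table layout carries the same label. In Table 12.6, remove *unadjusted* from both row labels so that the limits apply to QTcF only, in line with the text and footnote. Uncorrected QT remains in the descriptive summary already planned. The cost is two wording changes in the SAP, with no new data collection and no protocol amendment.

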14. CHANGES TO PROTOCOL-SPECIFIED ANALYSES

There are no changes from the protocol specified analyses.

16. APPENDICES

APPENDIX A: PRESENTATION OF DATA AND PROGRAMMING SPECIFICATIONS

General

- Specialized text styles, such as bold, italics, borders, shading, and superscripted and subscripted text will not be used in tables, figures, and data listings (TFLs) unless they add significant value to the TFL.
- Only standard keyboard characters are to be used in tables and data listings.
- Special characters, such as nonprintable control characters and printer- or font-specific characters, will not be used in a TFL.
- Hexadecimal character representations are allowed (e.g., μ , α , and β).
- All footnotes will be left justified and at the bottom of a page. Footnotes must be used sparingly and add value to the TFL.

Tables

- Means and medians will be presented to 1 decimal place more than the raw data. Standard deviations will be presented to 2 decimal places more than the raw data. Minimums and maximums will be reported with the same number of decimal places as the raw data. For parameters that are a mixture of raw and calculated values (for example height which can be either recorded in or converted to centimeters), the number of decimal places will be based on the raw data.
- Percentages will be presented to the tenths place.
- Unless otherwise specified, for frequency counts of categorical variables, categories whose counts are zero will be displayed for the sake of completeness. For example, if none of the subjects discontinue due to “lost to follow-up,” this reason will be included in the table with a count of 0. Categories with zero counts will not have zero percentages displayed.

- Lower and upper CI values must be presented to 1 decimal place more than the raw/derived data (i.e., to the same number of decimal places as the mean).
- Percentiles (e.g., 25% and 75%) must be presented to 1 decimal place more than the raw/derived data.
- For all inferential analyses, *P* values will be rounded to 4 decimal places (or at the highest level of precision) with a leading zero (0.0001). *P* values less than 0.0001 will be presented as “<0.0001.”
- The last footnotes will be:
 - “Source: xxx”, where xxx indicates the source table number(s), if applicable (in case aggregated results, such as the mean or median, are plotted), source listing(s) (in case individual responses are plotted), and/or source dataset(s) (e.g., ADaM).
 - “PROGRAM SOURCE: ...\\xx.sas, DATA CUTOFF DATE: DD Mmm YYYY, RUN DATE: DD Mmm YYYY hh:mm”.

Figures

- Legends will be used for all figures with more than 1 variable or item displayed. Treatment group sizes (n=xx) will be included, as appropriate.
- Figures will be in black and white but can be in color to add value to the clarity and readability of a figure. Lines must be wide enough to see the line after being copied.
- The last footnotes will be:
 - “Source: xxx”, where xxx indicates the source listing number(s) and/or source dataset(s) (e.g., ADaM).
 - “PROGRAM SOURCE: ...\\xx.sas, DATA CUTOFF DATE: DD Mmm YYYY, RUN DATE: DD Mmm YYYY hh:mm”.
- Line graphs over time of change from baseline results will include a horizontal dashed reference line at zero.

Listings

- If not otherwise specified, all data listings will be sorted by subject number, treatment, visit, and date/time, as appropriate.
- All date values will be presented in a SAS® statistical software, version 9.4 or higher (SAS Institute Inc) date format (e.g., 29AUG2001).
- All observed time values will be presented using a 24-hour clock format (HH:MM:SS) (e.g., 01:35:45 or 11:26). Seconds will only be reported if they were measured as part of the study.
- The last footnote will be “PROGRAM SOURCE: ...\\xx.sas, DATA CUTOFF DATE: DD Mmm YYYY, RUN DATE: DD Mmm YYYY hh:mm”.

Missing or Incomplete Dates

Adverse Events and Concomitant Medications

The most conservative approach will be systematically considered. If the adverse event (AE) onset date is missing/incomplete, it is assumed to have occurred during the study treatment phase (i.e., considered a treatment-emergent AE) except if the partial onset date or other data, such as the stop date, indicates differently. Similarly, a medication with partial start and stop dates could be considered as both a prior and concomitant medication.

The following algorithms will be applied to missing and incomplete start and stop dates:

Start Dates

- If the day portion of the start date is missing, then the start date will be estimated to be equal to the date of the first dose of test article, provided the start month and year are the same as the date of the first dose of test article and stop date is either after the date of the first dose of test article or completely missing. Otherwise, the missing day portion will be estimated as "01."
- If both the day and month portions of the start date are missing, then the start date will be estimated to be equal to the date of the first dose of test article, provided the start year is the same as the date of the first dose of test article and stop date is either after the date of the first dose of test article or completely missing. Otherwise, the event will be assumed to start on the first day of the given year (e.g., ??-??-2013 is estimated as 01-JAN-2013).
- If the start date is completely missing and stop date is either after the date of the first dose of test article or completely missing, then the start date will be estimated to be equal to the date of the first dose of test article. Otherwise, the start date will be estimated to be the first day of the same year as the stop date. All other non-AE and non-concomitant medication day calculations where only partial dates are available will be handled as follows: the first day of the month will be used in the calculations if the day part of a start date is missing, and January 1 will be used if both the month and day parts of a start date are missing.

Stop Dates

- If only the day of resolution is unknown, the day of resolution of the event will be assumed to be the last day of the month (e.g., ??-JAN-2013 will be treated as 31-JAN-2013).
- If both the day and month of resolution are unknown, the day of resolution of the event will be assumed to be the last day of the year (e.g., ??-??-2013 will be treated as 31-DEC-2013).

- If the stop date of the event is completely missing or event is continuing, the event resolution will be assumed to be after the first dose of test article, and the stop date will be imputed using the last known date on the study.

Medical History (including NTM History)

Missing day and month of the onset or end date of a medical history term (including NTM history) will not be imputed. However, if the month and year are present, the day will be imputed to 01.

Standard Calculations

Variables requiring calculation will be derived using the following formulas:

- Days: A duration expressed in days between 1 date (date1) and another later date (date2) is calculated using the following formula: duration in days = date2 – date1 + 1
- Height: Height entries made in inches are converted to centimeters using the following formula: height (cm) = height (in) × 2.54
- Weight: Weight entries made in pounds are converted to kilograms using the following formula: weight (kg) = weight (lb)/2.2046
- Temperature: Temperature entries in degrees Fahrenheit are converted to degrees centigrade using the following formula: temperature ($^{\circ}$ C) = $5/9 \times [\text{temperature} ($^{\circ}$ F) - 32]$
- Body Mass Index (BMI): BMI is calculated using height and weight using and is calculated using the following formula: BMI (kg/m^2) = weight (kg) / [[height (cm) / 100] 2]
- Change from baseline: Change from baseline will be calculated using the following formula: change = post-baseline value – baseline value

APPENDIX B: SAS PROGRAMMING QUALITY CONTROL REQUIREMENTS

Derived datasets are independently programmed by 2 programmers. The separate datasets produced by the 2 programmers must match 100%. Detailed specifications for the derived datasets are documented in the study analysis dataset specifications provided to the client at study conclusion.

Tables and listings are independently reprogrammed by a second programmer.

Listings are checked for consistency against corresponding tables, figures, and derived datasets.

The entire set of TLFs is checked for completeness and consistency prior to its delivery to the client by the lead biostatistician and a senior level, or above, reviewer.

Refer to TMP-SOP-0205-003 “QC Requirements” for further details.

APPENDIX C: TABLE, FIGURE, LISTING LAYOUTS

TLF mocks are contained in a separate document.

APPENDIX D: DMID ADULT TOXICITY TABLE

The DMID Adult Toxicity Table (21-NOV-2007) was modified to exclude the clinical component of the toxicity grading because clinical signs and symptoms related to abnormal laboratory values are not collected in this study. In addition, Grade 0 was added to the table so that shifts from normal could be analyzed. Grades for enzymes were modified as indicated in the table below.

For toxicity grades based on a multiple of the ULN, the normal range from the central laboratory will be applied.

For toxicity grades based on fixed values, the grades will be assigned regardless of the normal actual range values from the central laboratory. For example, a hemoglobin value of 10.0 gm/dL will be assigned a grade of 1 toxicity, even if the lower limit of normal from the laboratory was 9.8 gm/dL.

HEMATOLOGY					
	Grade 0	Grade 1	Grade 2	Grade 3	Grade 4
Hemoglobin (gm/dL)	> 10.5	9.5-10.5	8.0-9.4	6.5-7.9	< 6.5
Absolute Neutrophil Count (count/mm ³)	> 1500	1000-1500	750-999	500-749	< 500
Platelets (count/mm ³)	≥ 100,000	75,000-99,999	50,000-74,999	20,000-49,999	< 20,000
WBCs (count/mm ³)	1000-10,999	11,000-12,999	13,000-14,999	15,000-30,000	> 30,000 or < 1,000

CHEMISTRY

	Grade 0	Grade 1	Grade 2	Grade 3	Grade 4
Hyponatremia (mEq/L)	> 135	130-135	123-129	116-122	< 116
Hypernatremia (mEq/L)	< 146	146-150	151-157	158-165	> 165
Hypokalemia (mEq/L)	> 3.4	3.0-3.4	2.5-2.9	2.0-2.4	< 2.0
Hyperkalemia (mEq/L)	< 5.6	5.6-6.0	6.1-6.5	6.6-7.0	> 7.0
Hypocalcemia (mg/dL) (corrected for albumin)	> 8.4	8.4-7.8	7.7-7.0	6.9-6.1	< 6.1
Hypercalcemia (mg/dL) (correct for albumin)	≤ 10.5	10.6-11.5	11.6-12.5	12.6-13.5	> 13.5
Hypomagnesemia (mEq/L)	> 1.4	1.4- 1.2	1.1-0.9	0.8-0.6	< 0.6
Hypophosphatemia (mg/dL)	≥ 2.5	2.0-2.4	1.5-1.9	1.0-1.4	< 1.0
Hyperbilirubinemia (total bilirubin)	< 1.1×ULN	1.1-1.5×ULN	> 1.5- 2.5×ULN	> 2.5-5×ULN	> 5×ULN
	< 1.1×ULN	1.1-1.5×ULN	> 1.5- 3.0×ULN	> 3.0-6×ULN	> 6×ULN

ENZYMES

	Grade 0	Grade 1	Grade 2	Grade 3	Grade 4
AST (SGOT)	< 1.25×ULN	1.25-2.5×ULN	> 2.5-5×ULN	> 5-10×ULN	> 10×ULN
ALT (SGPT)	< 1.25×ULN	1.25-2.5×ULN	> 2.5-5×ULN	> 5-10×ULN	> 10×ULN
GGT	< 1.25×ULN	1.25-2.5×ULN	> 2.5-5×ULN	> 5-10×ULN	> 10×ULN
Alkaline Phosphatase	< 1.25×ULN	1.25-2.5×ULN	> 2.5-5×ULN	> 5-10×ULN	> 10×ULN
Lipase	< 1.1×ULN	1.1-1.5×ULN	> 1.5-2.0×ULN	> 2.0-5.0×ULN	> 5.0×ULN

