12.6 Safety Endpoint(s)

All safety data will be analyzed in the Safety Analysis Set. Adverse events will be coded using the Medical Dictionary of Regulatory Activities. The incidence of treatment-emergent adverse events will be presented by system organ class (SOC) and preferred term (PT), by SOC, PT and relationship to test article, and by SOC, PT and severity. Serious AEs and treatment-emergent adverse events that lead to discontinuation of the test article will also be presented by SOC and PT. Descriptive statistics for clinical laboratory, vital signs, and ECG parameters, including change from baseline, will be presented by timepoint collected and for the overall most abnormal post-baseline value (for clinical laboratory and vitals sign parameters). Incidences of potentially clinically significant clinical laboratory results, vital signs and ECG parameters as defined in the SAP, will also be summarized by timepoint collected and the overall most abnormal post-baseline value (for clinical laboratory and vital sign parameters).

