13.3 Clinical Laboratory Evaluation

Laboratory parameters (serum chemistry, hematology, and coagulation) will be summarized using descriptive statistics at baseline and at each post-baseline time point (the Day 28 and 84 visit, Day84/EOT) and for the most extreme (high and/or low) post-baseline value at any visit (including unscheduled results). Changes from baseline will also be summarized.

Select laboratory parameters will be graded according to the Division of Microbiology and Infectious Diseases (DMID) grading criteria, version 5.0. Incidence of potentially clinically significant (PCS) events (at least a 2-grade increase from baseline) will be presented by time point and for the most extreme post-baseline value at any visit (including unscheduled results).

The number and percentage (based on the number of subjects with a normal level at baseline) of subjects in each treatment group with an elevated transaminase (AST or ALT) level ($> 3 \times$ upper limit of normal [ULN], $> 5 \times$ ULN, and $> 10 \times$ ULN), an elevated bilirubin level ($> 1.5 \times$ ULN and $> 2 \times$ ULN) will be presented by study visit and at any post-baseline visit. A listing of subjects who meet the laboratory criteria for Hy's law at the same visit will also be provided. The laboratory criteria for Hy's law are defined as 1) ALT or AST $> 3 \times$ ULN, ALP $\leq 2.0 \times$ ULN, and total bilirubin > 1.5 ULN and 2) ALT or AST $> 3 \times$ ULN, ALP $\leq 2.0 \times$ ULN, and total bilirubin $> 2 \times$ ULN.

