APPENDIX E: DIRECTIONALITY OF WORST LABORATORY PARAMETERS

Laboratory Test	Parameter	Worst Value
Hematology	Hematocrit	Lowest value
	Red blood cell count	Lowest value
	Mean corpuscular hemoglobin	Lowest value
	Mean corpuscular hemoglobin concentration	Lowest value
	Hemoglobin	Lowest value
	Mean corpuscular volume	Lowest value
	White blood cell count	Lowest value
	Platelets	Lowest value

Laboratory Test	Parameter	Worst Value
	Eosinophils	Highest value
	Neutrophils	Lowest value
Chemistry		
	Alkaline phosphatase (ALP)	Highest value
	Alanine aminotransferase (ALT)	Highest value
	Aspartate aminotransferase (AST)	Highest value
	Blood urea nitrogen	Highest value
	Calcium	Both highest value and lowest value
	Chloride	Both highest value and lowest value
	Creatinine	Highest value
	Creatine phosphokinase (CK)	Highest value
	Gamma-glutamyl transpeptidase (GGT)	Highest value
	Lipase	Highest value
	Magnesium	Both highest value and lowest value
	Phosphorus	Both highest value and lowest value
	Potassium	Both highest value and lowest value
	Sodium	Both highest value and lowest value
	Total bilirubin	Highest value
Coagulation	Prothrombin time international normalized ratio (INR)	Highest value

[figure not shown]
Ptk0796-ntm-20203 SAP_v5.0

Final Audit Report

2024-09-23

Created:	2024-09-23
By:	[REDACTED]
Status:	Signed
Transaction ID:	CBJCHBCAABAAClSPMEgLPKs3xjls0INyRQi8ZVz_4_Mt

"Ptk0796-ntm-20203 SAP_v5.0" History

■ Agreement completed.

2024-09-23 - 2:31:33 PM GMT

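### Two SAP rules for potentially clinically significant (PCS) laboratory values fail as written: calcium grading needs albumin, which the listed panel lacks, and the worst WBC is the lowest value on a scale that grades mainly high counts

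*SAP*

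**What the plan says.** Protocol section 4 lists the incidence of PCS laboratory parameters as an endpoint under the primary safety objective. Protocol section 12.6 leaves the definition to the SAP ("Incidences of potentially clinically significant clinical laboratory results, vital signs and ECG parameters as defined in the SAP") and asks for the summary by timepoint and for "the overall most abnormal post-baseline value (for clinical laboratory and vital sign parameters".

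SAP section 13.3 gives the rule: "Incidence of potentially clinically significant (PCS) events (at least a 2-grade increase from baseline) will be presented by time point", and also for the most extreme post-baseline value, with unscheduled results included.

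The grades are in SAP Appendix D and the direction of the worst value is in SAP Appendix E.

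- **Calcium.** Appendix D has the row "Hypocalcemia (mg/dL) (corrected for albumin" and a matching hypercalcemia row, also adjusted for albumin. Appendix E takes calcium in both directions.
- **WBC.** Appendix D puts 1,000 to 10,999 in Grade 0, 11,000 to 12,999 in Grade 1, 13,000 to 14,999 in Grade 2 and 15,000 to 30,000 in Grade 3. Grade 4 is "> 30,000 or < 1,000". In Appendix E the row "White blood cell count" is assigned the lowest value only.

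For by-visit tables, SAP section 7 says: "If there is no nominal visit result, unscheduled visits that occur in the protocol defined window will be summarized instead".

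**The concern.** For calcium, the grading scale calls for a quantity that the listed panel cannot supply. SAP Appendix B requires two programmers' derived datasets to match exactly, but neither has a rule to program from. The calcium PCS counts would rest on an unrecorded choice.

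For WBC, the scale and the direction rule point opposite ways. Unless a count falls below 1,000, the most abnormal WBC on this scale is the highest one, and Appendix E discards it. The most-extreme summary could then show fewer subjects than a single visit column of the same output, although it should be at least as large as any of them.

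Unscheduled draws are the weakest spot. The most-extreme summary is where they are meant to be counted, and the by-visit summary uses them only in place of a missing nominal visit. A high WBC at an unscheduled draw could be absent from both.

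**Working it through.** The plan states no figure to reproduce here. The check is of consistency, followed by an illustration of size.

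**Calcium.** Protocol Table 1 (section 8.9.1) lists 27 items: 8 hematology, 17 chemistry, INR and β-hCG. Calcium is among the 17 and albumin is not. Appendix E has no albumin row. Neither document gives a correction formula or a fallback. Under the stated rule, no calcium grade can be derived from the listed panel.

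**WBC, logic.** Below 11,000 the only attainable grades are 0 and 4. With a PCS event defined as a rise of at least 2 grades:

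- From Grade 0, a rise to 13,000 or more is PCS. The lowest-value rule misses it whenever the lowest post-baseline count is 1,000 to 12,999. At a lowest value of 999 or of 13,000 the subject is flagged.
- From Grade 1, a rise to 15,000 or more is PCS. It is missed whenever the lowest count is 1,000 to 14,999.

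Examples with baseline 8,000 (Grade 0):

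| Post-baseline counts | Grade of lowest | PCS by lowest-value rule | Highest grade reached | PCS by highest grade |
|---|---|---|---|---|
| 8,000 and 16,000 | 0 | no | 3 | yes |
| 7,000 and 14,000 | 0 | no | 2 | yes |
| 9,000 and 31,000 | 0 | no | 4 | yes |
| 12,000 and 20,000 | 1 | no | 3 | yes |
| 13,500 and 16,000 | 2 | yes | 3 | yes |
| 900 and 8,000 | 4 | yes | 4 | yes |

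**WBC, size.** Protocol Appendix 1 schedules two post-baseline hematology draws, Day 28 and Day 84/EOT. For a subject with a Grade 0 baseline and both draws, the lowest-value rule counts a high-WBC event only if both qualify. Let p be the chance of Grade 2 or higher on the high side at one draw and r the between-visit correlation. The documents give neither, so both are assumed.

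- P(both) = p² + r·p(1 − p)
- P(any) = 2p − P(both)
- Share captured = P(both) / P(any)

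| p | r | P(both) | P(any) | Share captured |
|---|---|---|---|---|
| 2% | 0 | 0.0004 | 0.0396 | 1.0% |
| 2% | 0.5 | 0.0102 | 0.0298 | 34.2% |
| 5% | 0 | 0.0025 | 0.0975 | 2.6% |
| 5% | 0.5 | 0.02625 | 0.07375 | 35.6% |
| 10% | 0 | 0.0100 | 0.1900 | 5.3% |
| 10% | 0.5 | 0.0550 | 0.1450 | 37.9% |

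For 45 omadacycline subjects at p = 5%:

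- r = 0: 45 × 0.0025 = 0.1 shown, against 45 × 0.0975 = 4.4 with an event.
- r = 0.5: 45 × 0.02625 = 1.2 shown, against 45 × 0.07375 = 3.3 with an event.

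**Low counts.** The row "Absolute Neutrophil Count" has four grade steps, and Appendix E takes neutrophils at their lowest. At a WBC of 1,200, ANC is below 1,000 (Grade 2 or higher) unless neutrophils are at least 1,000/1,200 = 83% of the count. Low counts are therefore largely covered already, and WBC needs no extra low-side grades.

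**The case against.** **SAP 13.3 may govern.** It describes the most extreme value as high, low or both and does not cite Appendix E, so a programmer could include high WBC. But that wording is generic and has to be settled analyte by analyte. Only Appendix E does this, giving six electrolytes both directions and WBC the lowest only. If 13.3 was meant to prevail, Appendix E still needs correcting.

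**Albumin may be available.** The central laboratory may report it, and the laboratory manual, eCRF, dataset specifications and table shells are not in view. This stands as a limit: what is shown is that the protocol and SAP name no source and no formula. Appendix D does say that its clinical components were dropped because those data are not collected. The same adaptation was not made for albumin.

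**The capture figures rest on assumptions.** This also stands. At p = 5% and r = 0.8, P(both) = 0.0025 + 0.8 × 0.0475 = 0.0405 and P(any) = 0.0595, so 68% would be captured. A subject with a single post-baseline draw loses nothing. The contradiction between the two appendices does not depend on these figures.

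**The consequences are small.** They are. By-visit PCS still catches high WBC at both scheduled draws, raw summaries and listings remain, and Protocol 8.19.4 has clinically significant laboratory abnormalities recorded as adverse events.

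**Conclusion.** Both points hold. The WBC rule is wrong as written: applied literally, the most-extreme PCS summary drops a count of 16,000 that sits beside a normal draw, while the Day 28 column counts it, and this is not the most abnormal value that Protocol 12.6 promises. The calcium rule cannot be carried out from the documented panel. It is nearer to a missing specification than an error, since albumin may exist outside the documents seen.

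Under the assumed rates and correlations, the WBC summary would show roughly 1% to 38% of subjects with a high-WBC event at either scheduled visit, and more if the correlation is higher. The effect is confined to descriptive safety counts for two analytes, and no efficacy result depends on it. The correction should be made because the counts feed a listed safety endpoint and the cost is very low.

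**What to change.** - **Appendix E:** take WBC in both directions, as is already done for calcium, potassium and sodium. Count a subject as PCS in the most-extreme summary if either the highest or the lowest value meets the 2-grade rule. All four missed examples in the table above are then counted.
- **Appendix D:** state that calcium is graded on uncorrected total calcium. If albumin is already available from the central laboratory, name that source and the correction formula instead.

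This costs two wording edits in the SAP appendices and a small programming change. It needs no protocol amendment, added test or new low-WBC grades. The drawback is that uncorrected calcium may over-flag low values in subjects with low albumin, which a table footnote can state.
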